### Clinical Coordinating Center (CCC)

Clinical Coordination specific for the CriSP-TBI study will be performed by the LITES Network Clinical Coordinating Center at the University of Pittsburgh and [name] research staff and their dedicated research teams at the University of Pittsburgh, including all regulatory requirements, provider and coordinator training and monitoring.

### Data Coordinating Center (DCC)

Data Coordination specific for the CriSP-TBI study will be performed by the DCC and led by [name] at the Graduate School of Public Health at the University of Pittsburgh. The DCC will design data collection forms, build and maintain an electronic data management system, provide training and technical assistance for site-based data entry personnel, develop and implement quality control mechanisms (including in-person and remote monitoring), and produce reports. The DCC will also plan, coordinate, and carry out statistical analyses and make the datasets available for public use after the trial is completed.

## Data Management

**Data Sources:** Data will be collected prospectively as patient care progresses. This will include a review of the emergency medical patient care report(s), Emergency Department and electronic/ paper hospital records.

**Surveillance for Outcomes and Data Elements:** Data will be collected prospectively as patient care progresses. This will include a review of the medical patient care report(s), Emergency Department and electronic/ paper hospital records.

**Prehospital elements:** Mechanism of injury, prehospital vital signs including lowest GCS, lowest systolic blood pressure, highest heart rate, need for intubation/advanced airway, transported from scene, transported from referral hospital, ground transport, air medical transport.

**In-Hospital Data:** Demographics, shock severity (base deficit, lactate), injury characteristics, GCS and pupil exam, ED vitals, ED interventions (chest tubes, intubation), injury severity, operative interventions and timing of interventions, injury severity score, ICU days, ventilator days, length of stay, multiple organ dysfunction scores (daily), nosocomial infectious outcomes, blood gas results, x-ray reads, transfusion of blood and blood components, resuscitation requirements, all primary and secondary outcomes will be recorded.

**Data Entry:** The DCC will create an electronic data management system that will include a password-protected SSL website for data entry with built-in dynamic features such as data encryption, user authentication, range and data type checks, real time reports, data corrections tracking, and the capability to save and reload incomplete forms. The DCC will also draft a comprehensive data management manual that includes detailed instructions and provide training and technical assistance. Participants will be identified by a study ID only. Site will be required to store hard-copy source documentation separately in a secured, locked cabinet.

**Database Management:** A two-tiered database structure will be created. A front-end database will serve the web entry needs, using a database management system well-suited to handling updates from multiple interactive users. The data from this database will be transferred on a regular schedule to a data repository that can be used by statistical software packages. These datasets will be the basis for data queries, analyses, and monitoring reports. Various versions of this database will be kept as needed, e.g., for quarterly performance reports. Access to data will be limited to those who need access to perform their tasks. The database management system can manage large quantities of data, to merge data from multiple databases as required, to handle complex and possibly changing relationships, and to produce analysis datasets that can be imported into a variety of statistical analysis packages. Data will be backed up at regular intervals, with full transaction log files in use, and copies of the data will be stored offsite with a secure service. Servers will be migrated to a new host in the event of a hardware failure. All servers are behind an enterprise firewall and access must be granted through the firewall even within the University network.

## Human Participants

We anticipate that this study will be conducted under the federal provisions governing Exception from the Requirement for Informed Consent for Emergency Research, including community consultation, public notification, as well as notification of patients or their legally authorized representative as soon as feasible after enrollment. The latter shall include provision of an opportunity to opt out from ongoing participation that will be given through oral and written communication.

Capacity to provide informed consent will be assessed prior to randomization and will primarily be determined by Glasgow Coma Scale (GCS). Potential subjects with a GCS of less than 15 will be considered unable to consent. Potential subjects with a GCS of 15 will undergo a GOAT assessment, performed by a study investigator or neurosurgery CRC. A score of 74 or below will be considered unable to consent. For subjects that are determined to be unable to consent, assent will be obtained when applicable. The study team will also attempt to identify an appropriate LAR to provide prospective informed consent. If a LAR is identified within the 2-hour period after initial CT scan in the ED, this individual will be approached for proxy consent. If not, the patient will be enrolled under EFIC. If a potential subject has a GCS of 15 and scores 75 or above on the GOAT, we will presume s/he is capable of providing direct informed consent and will seek to obtain informed consent via a physician investigator.

Community consultation as determined by the IRB will be undertaken prior to final IRB approval. We will utilize the IRB at the University of Pittsburgh. Since the population eligible for enrollment includes all citizens in the study regions it will not be possible to target any small group. Feedback from the community will be obtained by research personnel regarding any concerns they may have about potential enrollment. If requested, bracelets will be made available that could be worn by members of the community who do not want to participate. Public notification and community consultation will be performed as directed by the IRB and may include such methods as surveys of the proposed study community, targeted small group meetings, or consultation with community leaders. Due to ongoing participation in numerous multicenter research studies involving emergency research, our institution and the other participating institutions have significant experience with community consultation and notification practices.

For additional details regarding the application of EFIC, procedures for notification and consent, and participant withdrawal, please refer to Appendix I – CriSP-TBI EFIC Plan.

### Study Stopping Points:

The following describes the study stopping points regarding participant involvement:

- 1) if the study procedures appear to be medically harmful
- 2) if the participant no longer wishes to participate
- 3) if the study is cancelled

**Institutional Review Board:** An IRB will be utilized at the University of Pittsburgh for the regulatory needs of studies.

**Training and Participating Site Coordination:** As the clinical coordinating center for the trial, the University of Pittsburgh will be collaboratively responsible for all research coordinator training, provider training and sample collection and storage. Research coordinators, providers and associated staff will be trained during the months prior to the trial start date regarding the scientific basis for the study, specific inclusion and exclusion criteria, sample collection and processing, study procedures and SOPs, and rapid TEG performance. Training verification and retraining will occur if new staff is hired. Trial enrollment and maintenance of data integrity will be assessed monthly using the web-based data platform. Trial screening, enrollment and data completeness and accuracy will be accessed at 6 months by the CCC.

## Safety Monitoring:

### Adverse Event definitions:

- a. Adverse event* means any untoward medical occurrence associated with the use of the drug in humans, whether or not considered drug related.
- b. Adverse reaction* means any adverse event caused by a drug.
- c. Suspected adverse reaction* means any adverse event for which there is a reasonable possibility that the drug caused the adverse event. Suspected adverse reaction implies a lesser degree of certainty about causality than “adverse reaction”
- d. Reasonable possibility.* For the purpose of IND safety reporting, “reasonable possibility” means there is evidence to suggest a causal relationship between the drug and the adverse event.
- e. Life-threatening, suspected adverse reaction.* A suspected adverse reaction is considered “life-threatening” if, in the view of either the Investigator (i.e., the study site principal investigator) or Sponsor, its occurrence places the patient or research participant at immediate risk of death. It does not include a suspected adverse reaction that had it occurred in a more severe form, might have caused death.
- f. Serious, suspected adverse reaction.* A suspected adverse reaction is considered “serious” if, in the view of the Investigator (i.e., the study site principal investigator) or Sponsor, it results in any of the following outcomes: death, a life-threatening adverse reaction, inpatient hospitalization or prolongation of existing hospitalization, a persistent or significant incapacity or substantial disruption of the ability to conduct normal life functions, or a congenital anomaly/birth defect.
- g. Reportable non-compliance* refers to a failure on the part of the investigator or study team member to follow the terms of the IRB approved protocol or abide by applicable laws or regulations, that adversely affect the rights and welfare of participants or significantly compromises the quality of the research data. Incidents of non-compliance on the part of the participant are not considered reportable.
- h. Unanticipated Problem Involving Risk to Subjects or Others (UPIRTSO)* refers to any accident, experience, or outcome that meets the following criteria: unexpected in terms of nature, severity or frequency; related, or possibly related, to a participant’s participation in research; and places participants or others at greater risk of harm (including physical, economic, or social) than was previously known or recognized.

**Assessing and Reporting Adverse Events (AEs):** Adverse events will be reviewed and assessed for relationship to the study intervention. Investigators and study team will determine if

any related adverse events occur during the period from enrollment through study participation termination. If reportable adverse events occur, they will be recorded on the adverse event case report form in the electronic data capture system. All reported adverse events will be classified by a) Severity (fatal or life-threatening, serious, or non-serious); and b) Expected vs.

Unexpected. An event will be determined to be unexpected if it is not consistent with the risks identified in the Investigator's Brochure or with the information provided in the general investigational plan or elsewhere in the IND application. Please refer to the table below for timelines for reporting.

This study population is expected to have many serious adverse events, including death from trauma related injuries. Expected adverse events that are related or possibly related to the intervention will be documented and reviewed for changes in nature, severity, or frequency across the study population.

Organization	Unexpected, fatal or life-threatening, suspected adverse reactions	Unexpected, serious, suspected adverse reactions	Expected adverse reactions	Reportable non-compliance	UPIRTSO
IRB	24 hours	10 working days	No reporting	10 working days	10 working days
FDA	7 calendar days	15 calendar days	No reporting	No requirement	No requirement
Dept of Defense	30 calendar days	30 calendar days	No reporting	30 calendar days**	30 calendar days*
DSMB	24 hours	7 calendar days	At next meeting (every 6 months)	At next meeting (every 6 months)	14 days*

\*reported based on IRB determination that event is UPIRTSO

\*\*reported based on IRB determination that non-compliance is serious or continuing

**Data Safety Monitoring Board (DSMB):** A Data and Safety Monitoring Board (DSMB) will be created to review this study and provide recommendations re. study continuation to the IND Sponsor. After initial approval and at periodic intervals (to be determined by the committee) during the study, the DSMB responsibilities are to:

- a. Review the research protocol, informed consent documents and plans for data and safety monitoring;
- b. Evaluate the progress of the study, including periodic assessments of data quality and timeliness, participant recruitment, accrual and retention, participant risk versus benefit, adverse events, unanticipated problems, performance of the trial sites, and other factors that can affect study outcome;
- c. Consider factors external to the study when relevant information becomes available, such

as scientific or therapeutic developments that may have an impact on the safety of the participants or the ethics of the study;

- d. Review clinical center performance, make recommendations and assist in the resolution of problems reported by the IND Sponsor or study site Investigators;
- e. Protect the safety of the study participants;
- f. Report on the safety and progress of the study;
- g. Make recommendations to the IND Sponsor, and if required, to the FDA concerning continuation, termination or other modifications of the study based on the observed beneficial or adverse effects of the treatment under study;
- h. Monitor the confidentiality of the study data and the results of monitoring;
- i. Assist the IND Sponsor by commenting on any problems with study conduct, enrollment, sample size and/or data collection.
- j. The DSMB will include experts in emergency medicine, surgery (trauma/critical medicine), bioethics and biostatistics. Members will consist of persons independent of the investigators who have no financial, scientific, or other conflict of interest with the study. Written documentation attesting to absence of conflict of interest will be required.
- k. The University of Pittsburgh Office of Clinical Research, Health Sciences will provide the logistical management and support of the DSMB. A safety officer (chairperson) will be identified at the first meeting. This person will be the contact person for serious adverse event reporting. Procedures for this will be discussed at the first meeting.
- l. The first meeting will take place before initiation of the study to discuss the protocol, approve the commencement of the study, and to establish guidelines to monitor the study. The follow-up meeting frequency of the DSMB will be determined during the first meeting. An emergency meeting of the DSMB will be called at any time by the Chairperson should questions of patient safety arise.

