**Study Intervention:**

**Study Intervention Arm:** Patients randomized to the intervention arm will receive an early infusion of urgent release cold stored platelets (CSP) once the patient is determined to meet all inclusion and no exclusion criteria. When clinically feasible, patients will undergo VerifyNow Aspirin or P2Y12 testing following initial platelet transfusion. Those patients who have not increased their respective ARU or PRU measurements to levels consistent with no drug effect (ARU > 550; PRU > 220), or who have another clinical indication for additional platelet transfusion, may undergo a second CSP infusion.

CSP infusion will occur once IV access is obtained irrespective of location. CSP infusion should be initiated first when possible but can be infused concomitantly with other transfusion requirements including packed red blood cells, plasma, or whole blood per institutional standard care. The administration will be begun by clinical staff.

**Standard Care Arm:** Patients randomized to the standard care arm will receive room temperature (RT) platelet transfusion per standard care at the University of Pittsburgh once the patient meets all inclusion and no exclusion criteria. When clinically feasible, patients will undergo VerifyNow Aspirin or P2Y12 testing following initial platelet transfusion. Those patients who have not increased their respective ARU or PRU measurements to levels consistent with no drug effect (ARU > 550; PRU > 220), or who have another clinical indication for additional platelet transfusion, may undergo a second RT platelet infusion.

**Randomization and Masking:** Individual patients determined to meet all inclusion and no exclusion criteria in the emergency department will be randomized and assigned according to a 1:1 ratio to CSP infusion or standard care using a permuted block design with variable block sizes of 4 and 6. The arm assignment will be provided in real time at the individual patient level by accessing an electronic randomization system. Backup envelopes containing randomization assignments will be available by contacting the Data Coordinating Center should there be any issues or failure of the electronic randomization system. Trauma and Neurosurgical attending and ED physicians will not be masked to treatment assignment as the study intervention is a blood product and full traceability is required. Arm assignment will be concealed to all outcome assessors performing the GOSE during follow-up.

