**Figure 2:**

1	Death	D
2	Vegetative state	VS
3	Lower severe disability	SD -
4	Upper severe disability	SD +
5	Lower moderate disability	MD -
6	Upper moderate disability	MD +
7	Lower good recovery	GR -
8	Upper good recovery	GR +

**Study Drug/Intervention:** Up to 2 cold stored apheresis units issued at the University of Pittsburgh will represent the CSP intervention. The volume of each unit will be approximately 200-300 mls and each will be stored in an FDA monitored approved refrigerator at 1-6 degrees Celsius for up to 14 days from preparation.

Please refer to the Investigator Brochure for additional details regarding CSP preparation, labeling, storage, dosing, and administration.

**Study risks and benefits:** Risks associated with blood component transfusion include infection, allergic reaction, fever, and respiratory distress. Additional risks associated with platelet transfusion include bacterial contamination, platelet alloimmunization, and hemolysis. Due to the higher activation in CSP as compared to RTP, there is a potential for increased risk of thrombotic complications. A detailed list of risks associated with the transfusion of platelets is included in the Investigator Brochure.

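### Adverse event form entry is filtered by an open-label relatedness judgement that does not fit the protocol's own definition, and infection data collected in everyone have no planned comparison by arm

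*Combined protocol and SAP*

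**What the plan says.** Under Adverse Event definitions, item a, an adverse event is "any untoward medical occurrence associated with the use of the drug in humans, whether or not considered drug related".

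The section Assessing and Reporting Adverse Events (AEs) then takes four steps:

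- It opens without a filter: "Adverse events will be reviewed and assessed for relationship to the study intervention".
- The investigators and study team are to determine whether "any related adverse events occur during the period from enrollment through study participation termination".
- Form entry is conditional: "If reportable adverse events occur, they will be recorded on the adverse event case report form in the electronic data capture system".
- For anticipated events: "Expected adverse events that are related or possibly related to the intervention will be documented and reviewed".

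On masking, Randomization and Masking states that "Trauma and Neurosurgical attending and ED physicians will not be masked to treatment assignment". The only people from whom the arm is said to be concealed are those scoring the GOSE at follow-up.

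Study risks and benefits names infection, allergic reaction, fever and respiratory distress for blood components in general. It continues: "Additional risks associated with platelet transfusion include bacterial contamination, platelet alloimmunization, and hemolysis". It also raises a possible increase in thrombotic complications with cold stored platelets. Among the in-hospital data elements under Data Management are "multiple organ dysfunction scores (daily), nosocomial infectious outcomes, blood gas results", with no condition on relatedness or arm.

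**The concern.** A definition that ignores causality is followed by a recording rule that depends on it. In an open-label trial, a relatedness judgement can be influenced by knowing which product was given. The direction is not obvious. Staff may be quicker to suspect an experimental product. Equally, the Specific Aims suggest that cold storage may make bacterial contamination less likely, which could lower suspicion.

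This population is expected to have many serious events from the injury itself. A harm of the product may then show only as a difference in frequency between arms, and a list already screened for suspected causation is a poor basis for finding one.

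Safety is one of the three things the pilot sets out to determine, some patients are enrolled under the exception from informed consent, and the results are meant to shape a larger trial. Named risks that depend on the filtered form would be the least reliably described.

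**Working it through.** No figure in the plan bears on this point, so the check is a comparison of texts.

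**1. Definition against recording rule.** Item a covers events of any cause. The reporting section reviews events in general, but what it requires to be determined, recorded or documented is limited to related, reportable, or related or possibly related events. No sentence puts an event judged unrelated on the form. *Reportable* is used in the definitions only for non-compliance. It might be read from the reporting timetable, but the adverse event columns there are all reactions or suspected reactions, so that reading brings back the causality condition.

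**2. Who judges, and against what.** No masked attribution or adjudication is described in the safety sections. Relationship is judged to the study intervention. The heading Study Intervention covers both arms, whereas Study Drug/Intervention describes the cold stored units and the synopsis names only those as the investigational drug. Whether room-temperature platelets count is therefore not settled.

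**3. Each named risk against its route outside the form.**

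| Named risk | Route outside the form | By-arm comparison planned |
|---|---|---|
| Thrombotic complications | Secondary outcome, primary admission, all enrolled patients | Yes |
| Allergic reaction | Secondary outcome, first 24 hours from arrival | Yes, in that window |
| Respiratory distress | In part: TRALI, within 6 hours of transfusion | Yes, for TRALI |
| Infection | Nosocomial infections, in-hospital data | None |
| Bacterial contamination | Only if recorded as a transfusion complication in the first 24 hours | Only within that outcome |
| Fever | As above | As above |
| Hemolysis | As above | As above |
| Platelet alloimmunization | None named | None |

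Of the 8 named risks, 1 is followed through the admission with a planned comparison. Another 2 have a planned comparison over a limited window or in part, and 3 depend on being classed as an early transfusion complication. The remaining 2 are infection, which is collected but not analysed, and alloimmunization, which has no other route (1 + 2 + 3 + 2 = 8). Death is covered separately: 24-hour mortality is the primary safety outcome and in-hospital mortality is a secondary one.

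**4. Analysis and oversight.** The chi-square comparison of binary outcomes applies to the listed outcomes. Infection is not in the Outcomes list, and the Statistical Analysis Plan names neither an infection comparison nor an adverse event comparison. Expected related events are to be reviewed for changes in frequency over the study population, with no mention of arm. The DSMB text does not require counts by arm.

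**The case against.** The strongest reply is that this is a deliberate and coherent design. The definitions are nested (event, suspected reaction, reaction), and a broad definition does not oblige a team to put every event on a form. Injured patients have many serious events, so the protocol collects the main harms as outcomes and keeps the form for suspected reactions. TRALI has an oxygenation and timing definition and is recorded even if its cause cannot be established. An independent DSMB evaluates adverse events and sets its own monitoring guidelines at its first meeting. The form itself, the data management manual and the Investigator Brochure are not in the documents and may say more.

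Much of this stands, and it limits the point. Three stronger readings are tempting but unsupported:

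- A reader might infer that harms are captured at all only when judged related. They are not: mortality, TRALI and thromboembolism bypass the filter in both arms.
- A reader might infer that infection cannot be compared fairly between arms. It can: nosocomial infections are collected for everyone, and the denominators are the randomized patients. What is missing is a planned comparison.
- A reader might take it as stated that relatedness assessors know the arm and that control-arm events are excluded. Both are inferences. The protocol names attending and ED physicians as unmasked, not the whole study team, and its wording on the intervention is ambiguous rather than exclusive.

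The reply does not supply a definition of reportable, a statement that the rule applies equally in both arms, a by-arm summary of infection or adverse events, or a route for late hemolysis, late fever or alloimmunization.

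**Conclusion.** The point holds in a limited form. Followed as written, the reporting section yields an adverse event form filtered by relatedness, at odds with the protocol's own definition, with no masked attribution described and an unclear position for control-arm events. By-arm counts from that form are open to attribution bias in either direction. Infection data exist in both arms but have no planned use in the safety comparison.

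The size is modest because the main safety endpoints do not depend on the form. It falls on infection, for want of a planned analysis, and on hemolysis and fever after the first 24 hours and alloimmunization, for want of another route. The documents give no event or attribution rates, so the bias cannot be quantified. The conclusion assumes that no unseen trial document defines reportable or sets a broader recording rule, and that at least some of those judging relatedness know the arm, as is likely in an open-label trial. This is a worthwhile low-cost correction, not a defect that undermines the trial.

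**What to change.** In Assessing and Reporting Adverse Events (AEs):

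- Define *reportable*, and reconcile the section with item a of the definitions.
- Record a short fixed list in both arms regardless of attribution: infection or sepsis, hemolysis, respiratory distress, transfusion reaction, thromboembolism and death.
- Keep relatedness as a separate field, used for expedited reporting.
- State that the same rule applies after room-temperature platelets.
- Late fever and alloimmunization are not on this list. Either add them or say that they are left to the relatedness-based route.

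In Outcomes, add the nosocomial infection data already collected as a safety outcome. In the Statistical Analysis Plan and the DSMB section, specify that the listed events and infections are tabulated by randomized arm for the DSMB and the final report.

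The cost is amendment wording and a modest rise in data entry. Most of the listed events are already abstracted, and unlisted trauma events need not be recorded. No extra staff or procedures are needed, and no clinical rule changes.

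### The safety reporting table gives fatal or serious expected reactions no expedited DSMB timeline, because severity is used only for unexpected ones

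*Combined protocol and SAP*

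**What the plan says.** Under Assessing and Reporting Adverse Events, the protocol sets up a two-way classification: "All reported adverse events will be classified by a) Severity (fatal or life-threatening, serious, or non-serious); and b) Expected vs" unexpected. Expectedness is judged against the Investigator's Brochure, the general investigational plan and the rest of the IND application: "An event will be determined to be unexpected if it is not consistent with the risks identified in the Investigator's Brochure". For timing, the reader is sent to the table: "Please refer to the table below for timelines for reporting".

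The table has two severity-graded columns, both limited to unexpected events: "Unexpected, fatal or life-threatening, suspected adverse reactions" (DSMB within 24 hours) and "Unexpected, serious, suspected adverse reactions" (DSMB within 7 calendar days). Expected adverse reactions have a single column. It asks for no reporting to the IRB, the FDA or the Department of Defense, and its DSMB cell reads "At next meeting (every 6 months)".

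Study risks and benefits names the risk that the product may raise: "Due to the higher activation in CSP as compared to RTP, there is a potential for increased risk of thrombotic complications". It refers to the Brochure for the detailed list of platelet transfusion risks.

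The DSMB section makes the chairperson the contact for reporting of serious adverse events and leaves the procedures to the first meeting (item k). It leaves meeting frequency to the committee and adds: "An emergency meeting of the DSMB will be called at any time by the Chairperson should questions of patient safety arise" (item l).

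**The concern.** The plan collects a severity grade for every reported event and then does not use it for the expected group. The reactions most closely tied to a mechanism the protocol itself describes, thrombotic ones above all, are the likeliest to be judged consistent with a listed risk. On the table's terms, a fatal pulmonary embolism suspected to be due to cold stored platelets, if judged expected, would have a slower DSMB timeline than a non-fatal serious reaction of an unlisted kind.

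What is at stake is how soon an independent body sees such a case and can advise the IND Sponsor. That matters more because some participants will be enrolled under the exception from informed consent.

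**Working it through.** The main check is textual; the plan states no figure to reproduce.

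**1. The DSMB row by severity and expectedness**

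| Severity | Unexpected, suspected | Expected |
|---|---|---|
| Fatal or life-threatening | 24 hours | Next meeting (six-monthly) |
| Serious | 7 calendar days | Next meeting (six-monthly) |
| Non-serious | No column | Next meeting (six-monthly) |

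The right-hand column does not vary with severity.

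**2. Where a listed risk falls.** The expectedness sentence asks about consistency with the reference documents and contains no explicit severity test. The definition of an unanticipated problem (Adverse Event definitions, item h) does include severity and frequency. Thrombosis is a named potential risk, so a thrombotic event would normally be classed as expected. The Brochure is not among the documents, so this rests on Study risks and benefits.

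**3. The column label.** Items b and c of the definitions separate an adverse reaction (caused by the drug) from a suspected adverse reaction (reasonable possibility). The unexpected columns use the second term and the expected column uses the first. Read strictly, an expected suspected reaction may have no column at all.

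**4. The other routes to the DSMB**

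- *Unanticipated problem.* The IRB is told within 10 working days and the DSMB within 14 days, with a footnote tying the DSMB report to an IRB determination. The event must be judged unexpected in kind, severity or frequency and must also show greater risk than was known. The IRB row asks for no reporting of expected reactions as such, so someone must first decide that the case belongs in this column. If both limits are used in full and the 14 days run from the determination, the path takes about 14 + 14 = 28 calendar days plus the IRB's own time.
- *Chairperson as contact for serious events (item k).* No scope or time limit is stated.
- *Emergency meeting (item l).* The chairperson must already know of the event.
- *Ongoing review of expected related events.* No reviewer and no interval are named.

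**5. Exposure between meetings.** Inputs: 100 patients and 2 years of enrollment (Protocol Synopsis), 1:1 allocation (Randomization and Masking), six months between meetings (table). Uniform accrual is assumed.

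- Accrual: 100 / 24 = 4.17 patients per month, or 4.17 / 2 = 2.08 on cold stored platelets.
- Maximum, for an event just after a meeting: 4.17 × 6 = 25 patients, 12.5 on cold stored platelets. That is 12.5 / 50 = 25% of the arm.
- Average, for an event at a random time in the interval: mean wait 6 / 2 = 3 months; 4.17 × 3 = 12.5 patients, about 6 on cold stored platelets.

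Exposure is proportional to the interval, so a different meeting schedule scales these figures directly.

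**The case against.** The strongest reply is that the table is not the whole system. A listed risk that proves fatal, or that clusters, can qualify as an unanticipated problem on severity or frequency and then has a DSMB deadline. The chairperson's contact role is not limited to unexpected events, and its procedures are set at a first meeting held before the study starts; they may already include prompt notice. Expectedness depends on a Brochure that cannot be seen here, and a potential for increased thrombotic risk need not make every fatal embolism expected.

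These points stand, and they rule out several stronger readings that a reader might infer:

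- *That such a case reaches the DSMB only at a six-monthly meeting, or that a cluster could not reach it sooner.* The other routes contradict this. What is missing is a stated time limit that applies without a prior judgement or an IRB step.
- *That thrombosis is expected by construction.* The documents make this likely but do not settle it.
- *That 25 patients would be spared.* This is a worst case, and notice alone does not stop enrolment. The DSMB recommends to the IND Sponsor (item g); it does not itself halt the trial.

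The reply does not remove the gap. The protocol sends its reader to the table for timelines, and there the fatal expected case has nothing faster than the next meeting.

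**Conclusion.** The point holds as a gap in the stated reporting rule and should be corrected. For a fatal or serious reaction consistent with a listed risk, the table offers the DSMB nothing between the 24 hours or 7 days given to unexpected events and the next meeting, up to about six months away. On a strict reading of the definitions it may offer no timeline at all.

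The exposure figures rest on uniform accrual, a six-month interval and no use of another route in the meantime. The interval is itself unsettled, since the table fixes it while the DSMB section leaves it to the committee. The benefit of correction is an earlier opportunity for a DSMB recommendation. The documents do not support a claim about the number of harms prevented.

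**What to change.** Amend the DSMB row of the reporting table:

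- Fatal or life-threatening suspected adverse reactions, expected or not, in either arm: notice to the DSMB chairperson within the existing 24 hours.
- Other serious suspected adverse reactions, expected or not, in either arm: notice to the chairperson within the existing 7 calendar days.
- Expected non-serious reactions: at the next meeting, as now.

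Leave the IRB and FDA rows unchanged. Relabel the expected column so that it covers suspected adverse reactions. Reconcile the table with the unanticipated-problem definition (item h) and with DSMB items k and l, including the six-monthly interval against the frequency left to the committee. If the first DSMB meeting already agreed a faster procedure, write it into the table.

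The cost is a short protocol amendment and some extra notices to the chairperson. The documents give no event rate from which to count them. Because only suspected reactions are covered, deaths attributed to the injury would not add to the load.
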